#### **10.0** Local Number of Participants

*10.1* Local Number of Participants to be Consented: 75 people will be consented and undergo the initial assessment for a minimum target of 30 participants completing the study.

#### 11.0 Local Recruitment Methods

11.1 Recruitment Process: Participants will be recruited through the Research Experience Participation (REP) program in the Psychology Department at the University of Minnesota. Study information will be available on the REP website. Research staff may introduce the study in relevant UMN courses and emails with study information may be distributed in relevant UMN courses. No students from [name] courses will be directly recruited by [name] or her graduate students, including [name]. Flyers and advertisements will be posted around the University of Minnesota campus, clinics, and hospitals, and surrounding area. Letters and brochures may be sent to local clinicians. Descriptions of the study may also be posted on websites, like ClinicalTrials.gov, StudyFinder, and http://radlab.umn.edu, and the University of Minnesota's Department of Psychiatry website

(https://sites.google.com/umn.edu/psychiatryresearch/home/depression/mindfulne ss-tdcs). We will also post advertisements on social media outlets (e.g., Facebook). Our recruitment materials may include a QR code or a link (https://z.umn.edu/mbttdcs) to our landing page. Upon scanning the QR code or clicking the link, users will be brought to a REDCap survey that describes the study and asks for contact information and birthdate. The REDCap landing page survey will be managed by project coordinators and will be independent from REDCap projects used for data collection. We will recruit participants from the Riverside Behavioral Health Outpatient Clinic using multiple strategies. First, patients in this clinic are invited to participate in a research recruitment registry. Our research staff will use the research registry to contact potential participants who have indicated they are interested in research using the contact information provided in the registry. Secondly, we will use a direct, in-person recruitment approach. Research staff will connect with providers in the clinic to discuss

patients who could be potential participants. For specific patients we will ask the provider to give an IRB-approved study brochure to the patient, along with a general introduction about the study. The research staff will be available to meet with the patient and their parent in the clinic to provide further information about the study; interested families will have the option to meet briefly with a researcher in person to allow face-to-face discussion, or to have the researcher follow up with them by phone. The Behavioral Health Research Recruitment Committee has approved this process.

- 11.2 Identification of Potential Participants: Potential research participants will self-identify in response to REP postings, flyers and advertisements, brochures, or other recruitment methods as listed above. Following this initial contact, a member of the research staff will screen the potential participant.
- 11.3 Recruitment Materials: See attached.
- 11.4 Payment: Participants will be compensated \$20 for the initial visit (consent/HIPAA & baseline assessment), \$15 for the baseline and posttDCS, and final EEG/ECG session, \$40 for the baseline and post-treatment MRI scan, \$5 for completing the home saliva samples and dairy at baseline and post-tDCS, \$10 for the post-tDCS assessment visit, \$15 for the final assessment, and \$5 for a week 1 assessment for a maximum total of \$185. If participants have to repeat a visit for any reason (e.g., poor data quality), they will be compensated accordingly for any repeated visits. Participants will not be compensated for intervention visits. If participants complete all in-person visits of the study, they will be entered into a \$50 raffle. A winner will be selected each time 3 participants complete the study. Participants may also choose to receive course extra credit as partial or total payment instead of cash (Research Experience Points) for their participation in this study (each ½ hour of assessment is worth 1 REP point). Cash payments will be made via institutional standard Greenphire ClinCard, a prepaid debit card that we can continue to load with money as the participants complete studies. In the case of early termination, the participant will receive partial payment. Parking passes will be provided when available.

#### **12.0** Withdrawal of Participants

12.1 Withdrawal Circumstances: Participants who have MRI or tDCS contraindications or participants who experience severe adverse events (e.g., seizure, suicide attempt, acute suicidality with plan of intent) or any unanticipated problem where the principal investigator feels it would be unsafe for the participant to continue may be withdrawn from certain

study activities or withdrawn from the entire study without their consent. In the case of other serious adverse events, the principal investigator or research staff will decide with the participant whether it would be safe or prudent for the participant to continue in the study based on their situation. Participants who experience mild to moderate adverse events (e.g., discomfort or other side effects like headache) will be allowed to discontinue at any point if they choose. Participants withdrawn from study participation due to an adverse event may be replaced to reach intended sample size. Participants will be withdrawn from the study if they appear to be unduly stressed.

- 12.2 Withdrawal Procedures: Participants may withdraw from the study at any time and study staff can withdraw a participant at any time if there are any serious adverse events. In the event of participant withdrawal, research staff may ask participants some questions about the study and/or to participate in some procedures or tests to help participants leave the study safely and/or to collect more information for the study. Information already collected prior to participant withdrawal will still be used. Participants who withdraw or do not qualify for the study after the phone screen may choose to receive referrals for psychological assessments.
- 12.3 Termination Procedures: In the case of a serious adverse event, researchrelated activities may be terminated immediately and appropriate treatment will be provide to the participant (e.g., first aid, emergency treatment, and follow-up care as needed). Care for such injuries will be billed in the ordinary manner to the participant or the participant's insurance company. Following termination, research staff may ask participants some questions about the study and/or to participate in some procedures or tests to help participants leave the study safely and/or to collect more information for the study. Information already collected prior to participant withdrawal will still be used.

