#### 5.0 Procedures Involved

5.1 Study Design: Participants will undergo ten daily sessions of one of two conditions: 1) active tDCS + Mindful Breathing Training or 2) sham tDCS + Mindful Breathing Training (approximate final n of 15 per group). A randomized block design will be used to assign each subject to a condition (sham or active tDCS). This study will be double-blind to +/- tDCS stimulation.

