Since we do not have pilot data with adolescents using either of these interventions, we were unable to conduct a power analysis to calculate an appropriate sample size. Budget and time constraints necessitate a relatively small sample size. While some studies in the literature have reported significant effects using similarly small samples, we cannot be certain that the study is powered appropriately to confirm or refute our hypotheses. Therefore, we have framed the project with a primary goal of establishing feasibility (our ability to recruit, adolescents' acceptance of randomization, adolescents' tolerability of the interventions) and of collecting data that will allow a power calculation to determine the sample size necessary for the federal grant to follow this work.

15.3 Statistical Analysis: A p-value of .05 will be used to determine significance for behavioral measures and a p-value of .005 will be used to determine significance for neuroimaging measures. Paired t-tests will be used to compare baseline versus post-tDCS and post-MBT intervention for both intervention groups for biological, clinical, and behavioral measures. Between-group t-tests will be conducted on the side-effects to examine group differences in prevalence of side effects. Feasibility will be determined by looking at descriptive statistics about enrollment and eligibility of people that express interest in the study and enroll as well as retention of enrolled participants. Correlation analysis will be conducted to assess how changes in clinical and behavioral relate to biological measures following intervention. Mixed repeated measures ANOVAs will test our hypothesis that the active tDCS group will show greater change than the sham tDCS group with condition (active or sham) as the between participant measures; within-participant measures will include behavioral.

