### **17.0** Provisions to Monitor the Data to Ensure the Safety of Participants

17.1 Data Integrity Monitoring: The principal investigator and/or co-investigator will monitor data quality for this study. They will ensure that data are generated, documented (recorded), and reported - in compliance with this

protocol, with Good Clinical Practice, and any other applicable regulatory requirements. Data will be stored in de-identified format. Study staff will monitor side effects forms and the CSSR-S for safety upon collection. Confidentiality may be broken in situations such as active suicidal ideation or other situations required by law.

17.2 Data Safety Monitoring. During all stimulation sessions, a member of the research staff will constantly monitor participants to ensure comfort and safety. A licensed clinical psychologist ([name]) or a supervising psychiatrist ([name]) will be contacted in the case of a clinical emergency to determine whether intervention is necessary. Emergency incidents will be documented and reported to the IRB. Documentation will include a description of the incident, action taken, and individuals involved. A 0 (No adverse event or within normal limits) to 5 (Fatal adverse event) rating scale will be used to evaluate the severity of adverse events and a 0 (Unrelated: The adverse event is clearly not related to investigational agent(s)) to 5 (Definite: The adverse event is clearly related to investigational agent(s)) will be used to determine the relationship between the adverse event and the proposed intervention. Any events rated 2 or higher will result in a notification to the supervising psychologist and events rated 3 or higher may warrant breaking the blind. Intervention will be determined by the supervising psychologist. Examples of incidents requiring immediate intervention and discontinuation from the study include active suicidal or homicidal ideation with plan, current self-harm requiring medical intervention, and a seizure. Data and safety monitoring will be discussed during weekly staff meetings with members of the research team to ensure that all adverse events are reported in compliance with the protocol, Good Clinical Practice, and other applicable regulatory requirements.

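### Adverse-event withdrawals may be replaced to reach a target set by finishers, and no post-treatment MADRS-S is secured from those withdrawn, so the depression comparison can become one of participants who stayed in

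*Combined protocol and SAP*

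**What the plan says.** Section 12.1 provides that "Participants withdrawn from study participation due to an adverse event may be replaced to reach intended sample size". The wording permits replacement without requiring it, and covers adverse-event withdrawals only. The same section adds a mandatory rule: "Participants will be withdrawn from the study if they appear to be unduly stressed". It gives no criterion for that state and does not mention replacement for it.

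The size to be reached is a count of finishers. Section 5.1 gives an "approximate final n of 15 per group", and section 10.1 says that "75 people will be consented and undergo the initial assessment for a minimum target of 30 participants completing the study". Section 5.3 places randomisation before the first stimulation visit, so any withdrawal caused by stimulation happens after randomisation.

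For the analysis, section 15.3 says "Mixed repeated measures ANOVAs will test our hypothesis that the active tDCS group will show greater change than the sham tDCS group", and section 15.1 applies repeated measures ANOVAs to MADRS scores before and after intervention. Paired t-tests within each group are also planned. Section 15 defines no analysis population, no method for missing outcomes and no rule for counting a participant who has been replaced.

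On data from withdrawn participants, sections 12.2 and 12.3 both state: "Information already collected prior to participant withdrawal will still be used". Questions or tests at exit are something that staff may request; no MADRS-S is scheduled.

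**The concern.** Three provisions combine. Recruitment continues until enough people finish. Participants who leave because of an adverse event can be made up by others. The planned tests can use only people with a post-treatment score. A randomised participant who is withdrawn during stimulation then drops out of the MADRS-S comparison, and the target is met by someone else who stayed.

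Replacement does not itself create the bias. Leaving randomised participants out of the comparison does that. Replacement makes the loss harder to see, because the final count still looks complete.

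Section 3.1 calls change in depression symptoms the primary clinical outcome, and section 15.2 says that the data will be used to size a later grant application. A distorted effect estimate would carry over into that calculation.

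**Working it through.** **1. The plan's own figures.** 2 × 15 = 30 agrees with section 10.1, and 30/75 = 40% of those consented. Section 15.2 reports no power calculation, and no dropout rate, SD or target effect is given, so there is nothing further to reproduce.

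**2. What remains of a participant withdrawn during the stimulation weeks.**

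| Data | Available? | Used by the planned analysis? |
|---|---|---|
| Baseline MADRS-S | Yes | Not without a post score |
| Interim MADRS-S (after 5 sessions) | Only if reached | Not in the pre/post ANOVA |
| Post-tDCS and final MADRS-S | Only if staff ask and she agrees | Needed, but not secured |
| Side-effect forms | Yes, up to withdrawal | Yes |
| Enrolment and retention count | Yes | Yes, since section 15.3 describes retention among those enrolled |

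The gap therefore lies in the efficacy comparison.

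**3. Whether the loss is ignorable.** Section 12.1 names suicide attempt and acute suicidality among the events that may lead to withdrawal, and adds undue stress. Section 17.2 says "Examples of incidents requiring immediate intervention and discontinuation from the study include active suicidal or homicidal ideation with plan". These reasons are close to what the MADRS-S measures. Section 17.2 also allows the blind to be broken for more severe events, so some staff decisions could be made with the arm known. Sections 12.1 and 17.2 describe overlapping events, one as a possible and the other as a required reason to stop; the sponsor should reconcile them.

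**4. Size of the efficacy bias (assumed inputs).** Let d be the share of an arm withdrawn without a post score, and D the outcome gap in SD units between those who stay and those who leave. The mean over all randomised in that arm is (1 − d) × stayers + d × leavers = stayers − d × D, so the completer mean is too favourable by d × D. The bias in the between-arm difference is

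d(active) × D(active) − d(sham) × D(sham).

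It is zero if the two products are equal, favours active if losses fall mainly there, and favours sham in the reverse case. The table takes losses in one arm only. The type I error comes from the noncentral t with 15 per arm and a two-sided 0.05 level (sidedness is assumed, because the plan does not state it).

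| d | D | Bias (SD) | Type I error |
|---|---|---|---|
| 5% | 0.5 | 0.025 | about 5.1% |
| 10% | 0.5 | 0.05 | 5.2% |
| 10% | 1.0 | 0.10 | 5.8% |
| 20% | 1.0 | 0.20 | 8.3% |
| 30% | 1.0 | 0.30 | 12.5% |

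For scale, 15 per arm has about 50% power (t-test) at the adult effect of g = 0.74 cited in section 2.3. A bias of 0.20 SD is 0.20/0.74 = 27% of that effect.

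**5. Dropout when all randomised participants are counted (assumed number k withdrawn and replaced, no other dropout).** The overall rate is k/(30 + k), and k/(15 + k) in one arm if all fall there: k = 1 gives 3.2% and 6.3%; k = 3 gives 9.1% and 16.7%; k = 5 gives 14.3% and 25.0%. With 30 participants, the chance of at least one adverse-event withdrawal is 26%, 79% or 96% if the individual risk is 1%, 5% or 10%.

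**The case against.** The other side has good points, and most of them limit the finding.

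- **Withdrawn participants are not excluded by rule.** A reader might infer that the analysed sample is by design those who tolerate treatment. The plan does not say so: earlier data are kept, an interim MADRS-S exists, and section 12.1 allows withdrawal from only some activities. This stands. The completer comparison is what the named tests yield by default when a post score is missing.
- **The bias need not favour active stimulation.** A reader might infer that active-arm withdrawals will be more frequent. Aim 2 expects equal tolerance, and section 13.1 calls adverse events rare and the common side effects mild. If active treatment works, suicidality could be commoner in sham, and its removal would work against active.
- **The dropout rate is not hidden by the text.** A reader might infer that replaced participants vanish from the count. Section 15.3 describes retention among enrolled participants, which includes anyone withdrawn after enrolment. Only an explicit sentence is missing.
- **Reuse of a vacated allocation is not described.** Section 5.3 assigns each subject 1:1 in randomised blocks, which on a plain reading covers replacements.
- **The stress rule is a participant protection**, and replacement is not written for it.
- **The stakes are those of a pilot.** Section 15.2 disclaims adequate power and puts feasibility first. At 5–10% withdrawal in one arm the type I error moves only to 5.1–5.8%.

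None of this supplies a post-treatment score for a withdrawn participant, or a method that can use incomplete data.

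**Conclusion.** The concern holds in a limited form. A finisher-based target, optional replacement after randomisation, tests that need a post score and no secured follow-up mean that the MADRS-S comparison can become one of participants who stayed in. Because some withdrawal reasons are close to the outcome, the missing scores may not be ignorable.

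Direction and size cannot be determined from the documents. Under the stated assumptions the effect is slight at 5–10% withdrawal in one arm (bias 0.025–0.10 SD) and material at 20–30% with a 1 SD gap (0.20–0.30 SD, type I error 8.3–12.5%). These figures assume losses in one arm only; similar losses in both arms would largely cancel. With 15 per arm, two or three withdrawals are enough to matter: 3 of 18 is 16.7% of an arm. The dropout and side-effect outcomes are recoverable with clear counting rules. The change is worth making because it is cheap and uses tools that the study already has.

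**What to change.** Leave the clinical withdrawal rules as they are and add a few sentences to sections 12 and 15:

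1. Invite everyone who stops stimulation or is withdrawn, if willing, to complete the remote MADRS-S at the scheduled interim, post-tDCS and final times. Section 5.2 already allows online questionnaires to be completed remotely.
2. Analyse MADRS-S in all randomised participants by assigned arm, including those withdrawn or replaced. Use a likelihood-based mixed model on all available scores in place of the complete-case ANOVA. Add a sensitivity analysis for outcome-related withdrawal, for example by worsening the unobserved scores over a stated range, separately by arm. The model gains little from a participant with a baseline score only, which is why item 1 is needed as well.
3. Report dropout and side effects by arm over all randomised participants, with staff-initiated and participant-initiated withdrawals shown separately.
4. Enter any replacement as a new randomisation at the next unused place in the sequence.

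The cost is a little more follow-up and analysis work, and possibly less favourable effect and dropout figures.

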#### 13.0 Risks to Participants

13.1 Foreseeable Risks:

**Transcranial Direct Current Stimulation (tDCS):** tDCS has shown to be a safe brain stimulation technique. Adverse events are rare with tDCS, and serious side effects have not been found following tDCS application. tDCS has been safely applied in psychiatry populations and in child and adolescent populations. The most common side effects are mild, including itching or discomfort under the electrode at the beginning of administration, headache, fatigue, dizziness, and nausea, which typically resolve at the end of stimulation. Our stimulation parameters will be within

established safety guidelines (Brunoni et al., 2011). There have been reported incidents of treatment-emergent hypomania and mania in unipolar and bipolar depression patients following tCS (Matsumoto et al., 2017). As such, we will rule out participants with bipolar disorder and will use the MINI to screen out participants with symptoms of mania and to monitor participants for any change in manic symptoms over the course of the study. These risks will be described to the participants during the consent process and participants may choose whether to participate or not. Participants may decide to withdraw from the study at any point.

**MRI Scanning:** MRI scanning will be conducted using a 3 Tesla Siemens Prisma MRI machine. The magnet in the scanner may cause electronic devices like watches to malfunction, and some metal objects can be pulled into the scanner. Participants will be screened prior to the scan to make sure they have nothing in their body which could be magnetic or affected by the magnetic field of the scanner. Participants will be asked to change into scrubs to ensure they have no metal on their person.

It may be uncomfortable lying still in the scanner for the amount of time required. The participant may experience some stiffness and soreness in the muscles from being still. To make participants as comfortable as possible, we will provide soft pads to help support the next, back, and legs.

The scanner itself makes a lot of noise while it is running. This can be uncomfortable and may affect the participant's hearing. Participants will be asked to wear ear plugs which will significantly reduce the amount of noise. Participants will also be wearing headphones in addition to the earplugs to allow them to hear the investigators and listen to music.

Some people may become uncomfortable in the scanner because they are not comfortable being in enclosed spaces. We will screen for claustrophobia before we bring the participant to the scan center. They will have the option of using a mock scanner prior to going into the scanner to assess their level of comfort. They will not be required to participate in the scan or continue the scan if they are uncomfortable.

If a participant has a positive pregnancy test, they will not be scanned. We will not inform the participant's parent of the results unless we feel the pregnancy would cause serious problems for the participant. Adult participants will be notified of their pregnancy test results, if positive. We may also obtain a false positive with the urine toxicology screen or pregnancy test. We will inform participants of the risk of obtaining a false positive and encourage them to follow up with their primary care

physician. If the toxicology screen is positive, results will be noted on the MRI CRF form and the participant will continue on with the MRI scan.

There is a chance we might find something abnormal when we look at the images of the participant's brain. We will send all images to a trained radiologist after the scan so they can be assessed for abnormalities. These images will not have any identifying information about the patient. If the radiologist recommendation is to further investigate the unusual results of the pictures, the investigator will contact the participant. The participant is responsible for further evaluation and follow-up in response to any MRI incidental findings.

**Clinical Assessments**: Participants may also experience mild stress, discomfort, or fatigue during the clinical assessment or while completing self-report or behavioral assessments. The assessments may involve questions about feelings, past experiences, and family history. Participants are encouraged to only share what they feel comfortable with and will not be induced to discuss anything that will make them too uncomfortable. The results of this study may be published and/or presented, but identifying information about participants will not be released unless required by Federal Law.

**Behavioral Tasks**: These tasks may be tiring. Some tasks may ask participants to think about negative thoughts or involve negative stimuli that may cause mild stress, discomfort, or fatigue.

**Suicide/Self-Injury Risk**: The population being researched in this study has a higher risk for suicidal ideation, suicide attempts, and serious injury due to depression. The research team will monitor depression (MADRS-S), suicidal ideation (C-SSRS), and self-harm behaviors (C-SSRS) at baseline, midway through the intervention assessments at the interim assessment, and post-intervention. Answers will be reviewed by the clinical assessor who is trained and supervised by a licensed psychologist. Participants who indicate suicidal ideation or significantly increased self-harm behaviors based on the C-SSRS will be asked to meet with one of the investigators of the study to assess risk.

Participants with suicidal ideation with no plan or intent who agree to a safety plan (either developed with the investigator or a pre-existing safety plan) will be allowed to continue in the study. The investigator will inform parents of the discussion and safety plan (if applicable).

Participants with severe self-harm (requiring stitches or

hospitalization), suicidal ideation with intent, or those who cannot or will not agree to a safety plan will be escorted to the Emergency Room located 1 floor below the Ambulatory Research Center (ARC) in the West Building of the Fairview Riverside Hospital.

**EEG/ECG:** Mild skin irritation may occur at the electrode placement site (e.g., redness).

- 13.2 Reproduction Risks: The effects of tDCS, EEG and MRI scans on the unborn fetus are not known, and participating females should not be pregnant. Pregnant participants will not undergo the stimulation, EEG or MRI scans. Participants and parents if participants are under the age of 18 will be told that the participant should not undergo study procedures if there is a pregnancy or possibility of a pregnancy. Participants will be informed about pregnancy risks during the consent process and will be encouraged to use a reliable form of birth control. Participants will take a mandatory pregnancy test before each MRI scan. If the urine pregnancy test is positive, the participant will not undergo the MRI scan or any tDCS sessions. If the pregnancy test is positive at the post-tDCS session, participants will not undergo the MRI scan but may choose to complete the 3-week at-home / in-person MBT training and clinical assessments. Participants will be asked to inform study staff at any other point of the MRI and tDCS visits if they have any concerns that they may be pregnant. Additional pregnancy tests can be offered at any point during other visits. Pregnancy and toxicology screens will be conducted at the CMRR by research staff. Participants will provide urine samples and we will use a pregnancy test strip (Clarity Diagnostics; Manufacturer # DTG-HCG100) to test for pregnancy and an Integrated E-Z Split Key Cup Urine Drug Screening with Adulteration for 5 Drugs for the toxicology screen (Manufacturer # DUD157023019). Both of these tests have a CLIA waiver (see attached materials for more details on the tests and for CLIA waiver documentation). These tests will be purchased through UMarket. Results will be recorded on CRF forms for MRI scanner sessions. Urine will be disposed of by being flushed down the toilet and used testing materials will be disposed of in the garbage.
- *13.3* **Risks to Others**: There are no anticipated risks to others who are not participants.
- 13.4 Email Risks: Participants will be able to opt in to communicating with study staff via unencrypted email to arrange their appointments and receive study instructions. There are risks associated with email communication, and these risks increase when the emails are sent without an encryption

service. Risks of sending or receiving emails without encryption include, but are not limited to:

- Others can intercept messages.
- If messages are sent or received on an employer-owned device, the employer may have the right to save and read the messages. The internet or cell-phone provider may also have the right to save and read email messages.
- A copy of the messages may be saved on a device or computer system, even if it is deleted.
- If an email address is not typed correctly, it can be sent to the wrong person.
- Emails can spread computer viruses.
- Others may be able to access messages on devices that were lost, stolen, or thrown away.
- If a user changes emails without notifying study staff, they may miss communications.

13.5 **Text Message Risk:** Participants will be able to opt in to communicating with stud staff via text message to arrange their appointments and receive study instructions. There are risks associated with communication via text message. Risks of sending or receiving text messages include, but are not limited to:

- Others can intercept messages
- Text messages may be viewed by University of Minnesota staff depending on the nature and timing of said messages, and may be monitored by the University to ensure appropriate use.
- If messages are sent or received on an employer-owned device, the employer may have the right to save and read the messages. The cell-phone provider may also have the right to save and read text messages.

